4.2. Secondary endpoints

- Number of current drug treatments
- History of falls
- Age

5. **METHODOLOGY / RESEARCH DESIGN**

5.1. RESEARCH DESIGN

Prospective multicenter cohort study

Recruiting centers: Geriatrics Center of Southern Ile-de-France Hospital Group

- Melun Hospital
- EHPAD Melun
- EHPAD Brie-Comte-Robert

6. **STUDY POPULATION / ELIGIBILITY CRITERIA**

6.1. INCLUSION CRITERIA

- Patients over 75 years of age cared for by the geriatrics unit of Southern Ile-de-France Hospital Group (either hospitalized or institutionalized).
- Patient able to understand a questionnaire in French
- Patient able to answer a questionnaire in French
- Patient able to stand up
- Patient able to consent

6.2. NON-INCLUSION CRITERIA

- Patient who has had lumbar surgery at some time in his or her life
- Patient under guardianship
- Patient opposition
- Patient with cognitive disorders assessed during hospitalization

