1. ABSTRACT

The impact of pelvic joint stiffness on the fear of falling in subjects over 75 years of age, hospitalized or in an institution. Study of a cohort of 100 patients.

JS (joint stiffness associated with fear of falling)

Background:

Purpose:

Fear of falling is one of the most concern in geriatric medicine. It could modify the daily activities of the elderly and create secondary troubles like sarcopenia, depression, it decreases the quality of life for this population.

Abstract: Fear of falling is defined as the enduring preoccupation with falling, leading the person to avoid activities that they are capable of doing. It modifies its behavior and affects its quality of life, its well-being and increases the risk of developing pathologies linked to the lack of physical activities. Joint stiffness is a major disorder in the elderly linked to bone and joint aging, but also to lack of mobilization. The pelvic girdle is the mechanical structure at the center of the balance and gait systems. The lack of amplitude of the joints that compose it could induce a fear of falling.

This study seeks to highlight whether there is an association between the fear of falling and the lack of amplitude of the different joints of the pelvic girdle.

Primary outcome:

Highlight a significant positive association between the Schober index (quantitative) and / or hip flexion goniometry (quantitative) and / or hip extension goniometry (quantitative) with the FES-I score (qualitative 2 groups).

Secondary outcomes: - Validity of 3 FES-I categories according to anthropometric measurements

- Evaluation of the linearity of the association
- Assessment of the strength of association
- Impact of cofactors collected on FES-I (polypharmacy, history of fall)

Study design: description of the main features of the research according to type of research

Eligibility criteria:

inclusion criteria:

- over 75 years old
- Ability to understand and answer a questionnaire in French
- Ability to stand up
- Patient from the Melun hospital (santé pole center+ nursing home of the GHSIF)
- Affiliated with a social security scheme

exclusion criteria:

- mental disorders, lumbar surgery

Interventions: Procedure: Study of a cohort of 100 patients

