2.5. EXPECTED BENEFITS

Fear of falling is a major concern in elderly patients. The risk factors identified are social, psychological, linked to a history of falls or the use of medication. This fear restricts physical activity and reduces quality of life.

The pelvic girdle is central to our postural balance. Its suppleness guarantees the proper adaptation of our static and dynamic body schema.

Aging can lead to osteoarticular stiffness and connective tissue fibrosis, a reduction in range of motion and thus a loss of proprioceptive adaptation of the pelvic girdle. By identifying joint stiffness as a risk factor for fear of falling, we can treat this factor and influence the fear of falling. Elderly patients regain confidence, their fear of falling diminishes and they are encouraged to resume physical activity gradually and at their own pace.

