3. RESEARCH OBJECTIVES

3.1. MAIN OBJECTIVE

To demonstrate a significant association between the Schober index (quantitative) and/or hip goniometry in flexion (quantitative) and/or hip goniometry in extension (quantitative) with the FES-I score (qualitative 2 groups).

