4. EVALUATION CRITERIA

4.1. MAIN EVALUATION CRITERION

FES-I questionnaire

This questionnaire comprises sixteen items. It is an improved version of the Fall Efficacy Scale (FES) proposed by Tinetti (18). The FES-I was developed by the Prevention of Falls Network Europe (ProFaNE). It is available on the ProFaNE website. A version of the FES-I scale has been translated into French. The questionnaire works as follows: for each proposition (16 in all), respondents are asked to rate their level of anxiety when imagining themselves carrying out the corresponding action. For each item, the respondent's level of concern is rated on a scale from 1 to 4, with the following correspondences:

- 1 not at all worried;
- 2 a little worried;
- 3 quite worried;
- 4 very worried.

The final score for this test is therefore between 16 and 64. The higher the score, the greater the fear of falling. The cut-point for this questionnaire, defining a high level of apprehension about falling, is set for scores greater than or equal to 28, according to research by (Delbaere et al, 2010)⁵

Hip goniometry

Hip goniometry: expressed in degrees, measures hip joint amplitude in active flexion and extension using a goniometer. The measurement is taken standing up. We evaluate one hip, the one that appears most mobile to the patient. With the goniometer at the level of the greater trochanter, we ask the patient to actively flex the hip, knee bent, checking that the lumbar vertebrae are not engaged. Same procedure on the same leg for straight-leg hip extension.

Modified Schober index

Modified Schober Index: This test is used to identify patients with ankylosing spondylitis (Macrae & Wright, 1969)⁶ and assesses lumbar joint mobility in flexion. Subsequent studies have shown the test to be reliable and reproducible (Koppenhaver *et al.*, 2011)⁷, (Malanga *et al.*, 2005)⁸.

- When the patient is standing, a first mark is made at the sacro-lumbar junction or between the posterior-superior iliac spines;
- a second mark is made 10 cm above the sacro-lumbar junction;
- a third mark is made 5 cm below the sacro-lumbar junction;
- a measuring tape is stretched between the three marks and the distance between the first and third marks is recorded, in neutral position and at maximum flexion of the lumbar spine;
- a deviation of less than 5 cm is considered pathological.

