12. QUALITY CONTROL AND ASSURANCE

12.1. DATA COLLECTION INSTRUCTIONS

All information required by the protocol must be recorded in the observation notebooks, and any missing data must be explained. Data should be collected as they are obtained, and transcribed neatly and legibly into the notebooks.

Erroneous data recorded in the observation notebooks should be clearly crossed out, and the new data should be copied next to the crossed-out information, accompanied by initials, date and, where appropriate, a justification by the person directing and supervising the research, or the authorized person who made the correction.

For the purposes of this study, data will be collected on a paper observation notebook.

Data collection will be carried out by: the investigator at each site

Data will be collected during the patient's stay and hospitalization.

The data collected in this study will be:

- Age
- gender
- History of falls
- Number of current drug treatments
- FES-I questionnaire score
- Hip goniometry in flexion
- Hip goniometry in extension
- Lumbar schober index

The data used in this study will come from: patients' medical records, the FES-I questionnaire and the measurements taken.

In order to carry out this study, pseudonymized data will be transmitted to the promotion unit of the clinical research unit

12.2. IDENTIFICATION OF DATA COLLECTED DIRECTLY IN THE CASE REPORT FORMS, WHICH WILL BE CONSIDERED AS SOURCE DATA

The observation book data used as source data are:

- FES-I score
- Schober index
- Hip goniometry in flexion
- Hip goniometry in extension

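### Past lumbar surgery is excluded, but past hip surgery, prosthesis or fracture is neither excluded nor recorded, so it may confound the two hip-range comparisons, with only partial protection elsewhere in the plan

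*Combined protocol and SAP*

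**What the plan says.** The only surgical exclusion in section 6.2 is "Patient who has had lumbar surgery at some time in his or her life". The abstract's exclusion line reads "mental disorders, lumbar surgery" and has no hip item either.

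The main objective (section 3.1) names three measures: the Schober index, and "hip goniometry in flexion (quantitative) and/or hip goniometry in extension (quantitative) with the FES-I score". Section 9 compares each between FES-I below 28 and FES-I 28 or more by a Mann-Whitney test, without adjustment.

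Section 12.1 lists eight items: age, gender, falls history, "Number of current drug treatments", the FES-I score and the three measurements. Hip history is absent, and so is the side measured.

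Three other provisions bear on the point:

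- Section 4.1, on the choice of hip: "We evaluate one hip, the one that appears most mobile to the patient". It also fixes the position: "The measurement is taken standing up".
- Section 8.8 stops patients who are unable or unwilling to perform a measurement.
- Section 9 plans Mann-Whitney tests separately in patients with and without previous falls. These are secondary, run only if fall rates differ significantly between the FES-I groups, and depend on the numbers available.

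**The concern.** By excluding lumbar surgery, the plan accepts that past surgery can spoil a mobility measurement. It applies that reasoning to the spine and not to the hip, where two of its three measurements are taken.

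The population makes this relevant. A hospitalised patient over 75 who is recovering from a hip fracture is eligible if able to stand, answer the questionnaire and consent. The event can reduce hip range, and the fall behind it can raise fear. Section 2.5 itself describes known risk factors as "linked to a history of falls or the use of medication". The plan has a different route in mind: sections 2.2 and 2.5 describe stiffness from ageing and from muscular or rheumatic disease, acting through proprioception, and foresee treating that stiffness to reduce fear.

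If a hip association is found, readers will ask how much of it comes from patients with a past hip event. There is one visit and no follow-up, and the dataset as planned cannot answer.

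**Working it through.** **1. The plan's own figure.** Section 2.1.4 gives 100 patients for 90% power at 5% risk, with no effect size, SD, group split or sidedness, so it cannot be reproduced. Solving backwards for one two-sided test with equal groups:

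d = (1.960 + 1.282) × √(1/50 + 1/50) = 3.242 × 0.2 = 0.65 SD.

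This serves only as a yardstick below.

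**2. Assumed inputs.** The documents give none of these:

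- prevalence p of a past hip event: 20% or 30%;
- range of an affected hip: 1 SD lower;
- probability of FES-I 28 or more: 0.8 with an event, 0.5 without;
- no link between stiffness and fear within either set of patients;
- share s of event patients whose *measured* hip is the affected one: 1, 0.5 or 0.25.

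**3. Spurious difference between groups.** Write A for FES-I below 28, B for 28 or more, and E for a hip event. The expected difference in SD units is 1 × s × [P(E|B) − P(E|A)].

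- p = 0.2: P(B) = 0.2×0.8 + 0.8×0.5 = 0.56. P(E|B) = 0.16/0.56 = 0.286; P(E|A) = 0.04/0.44 = 0.091. Difference = 0.19 × s.
- p = 0.3: P(B) = 0.3×0.8 + 0.7×0.5 = 0.59. P(E|B) = 0.24/0.59 = 0.407; P(E|A) = 0.06/0.41 = 0.146. Difference = 0.26 × s.

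Even with s = 1 this is well below the 0.65 SD of step 1. Halving s halves it.

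**4. False-positive rate.** Simulated: N = 100, one two-sided Mann-Whitney test at 0.05.

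| Measured hip is the affected one | p = 20% | p = 30% |
|---|---|---|
| always | about 13% | about 20% |
| in half of event patients | about 7% | about 9% |
| in a quarter | about 5% | about 6% |

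The nominal rate is 5%.

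**5. Sensitivity to the assumptions.** With the measured hip always affected:

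- 10% prevalence gives about 6–8%;
- a probability of 0.65 instead of 0.8 gives about 7% and 8–9% at 20% and 30% prevalence;
- a 1.5 SD shift at 30% prevalence gives about 32–35%.

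**6. Cost of leaving these patients out.** Keep d = 0.648 and equal groups; power = Φ(d × √(n/2) − 1.960), with n per group.

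- n = 50: Φ(3.242 − 1.960) = 90%.
- n = 40 (20% removed): Φ(2.899 − 1.960) = 83%.
- n = 35 (30% removed): Φ(2.712 − 1.960) = 77%.

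**The case against.** A reader might infer that a fall-related hip event can by itself produce the association the study seeks. The documents do not support that.

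- **Choice of hip.** The more mobile hip is tested, so a one-sided fracture or prosthesis will often be on the other side. The table shows how far this matters: the inflation is material only when the measured hip is itself affected. Even the worst case shown (1.5 SD) leaves about two-thirds of studies negative.
- **Ability to perform the test.** The hip tests are active and done standing, and section 8.8 stops patients who cannot do them. The most limited patients therefore leave the study.
- **Falls history.** It is collected, so it would be too strong to say that the study has no means of checking. If the history covers lifetime falls, the stratum without falls contains no fall-related hip events.
- **Aim.** The main objective is an association. A prosthesis placed for rheumatic hip disease may lie within the hypothesis of section 2.2, so excluding every such patient would go too far.

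All of this stands as mitigation, but none of it closes the gap. Bilateral events, and patients who judge the operated hip the more mobile, are not covered. When the good hip is tested, the operated leg may have to bear weight. Because the side is not recorded, the protection cannot be verified. The falls analysis is secondary and conditional, has no stated look-back period, and would miss an elective prosthesis.

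**Conclusion.** The asymmetry is plain in the text: the plan protects the lumbar measure from past surgery and leaves the two hip measures unprotected, with no variable to examine the matter later. Unrecorded hip history is a possible confounder of the two hip comparisons, and existing provisions mitigate it only in part. The Schober comparison is not directly affected.

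The size is unknown, because the documents give neither the prevalence of hip events nor their effect on range or fear. The calculations are illustrations. They run from a rate close to nominal, when the measured hip is seldom the affected one, to 13–20% when it always is at 1 SD. The point does not invalidate the design. It is a cheap improvement that must be made before data collection.

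**What to change.** - **Section 12.1:** add one line, taken from the medical file already opened to check eligibility (section 6.3): hip surgery, hip prosthesis, or hip or pelvic fracture (yes/no, side, date). Also record which hip was measured.
- **Section 9:** add a sensitivity analysis repeating the two hip comparisons without patients who have such a history. Report the estimated difference between FES-I groups with its confidence interval beside the main result, and interpret the hip association in that light.
- **No significance rule:** do not require the restricted result to remain significant before crediting stiffness. With 20–30% of patients removed, power falls from 90% to about 83–77%, so a true association could be disowned merely through lost numbers.

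The sample size and eligibility criteria do not change. The cost is the added notebook entries, one extra analysis, and lower precision in that analysis.

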6.3. RECRUITMENT PROCEDURES

Patients are recruited during a follow-up consultation during their hospitalization, or during their stay for EHPAD patients, at the suggestion of the therapeutic team, from among patients cared for by Southern Ile-de-France Hospital Group geriatrics unit.

Patients will be informed individually and given an information note to read. If they so wish, they will be offered a two-day cooling-off period, and if they agree to take part (non-objection) they will be able to ask any questions they may have before deciding to take part in the study. Inclusion and non-inclusion criteria will then be checked in the medical file (age, existence of cognitive disorders, etc.).

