2.1.3. DESCRIPTION AND RATIONALE OF THE STUDY POPULATION

The aim of this study is to determine whether the intensity of joint stiffness is associated with high apprehension of falling in elderly patients.

We chose to carry out the study in this population because: hospitalized patients or residents of Residential Care Facility for Dependent Elderly People (EHPAD in French) are at greater risk of fear of falling.

2.1.4. JUSTIFICATION FOR THE DURATION OF THE STUDY.

A retrospective analysis of observational data carried out on a sample drawn from a similar population enabled us to calculate the minimum number of subjects required to demonstrate a statistically significant association between the reference test and at least one of the variables studied. It is worth noting that 100 patients are required to reject the null hypothesis of the primary objective with 90% power and 5% risk. Given the number of geriatric patients at the Southern Ile-de-France Hospital Group (GHSIF), a 6-month period is planned to reach the number of patients required for this study.

Once a patient is included in the study, the total duration of his/her participation is 30 minutes. Inclusion and evaluation of patients is carried out progressively over the course of the study.

The total duration of the study is therefore estimated at 6 months.

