2.3. JUSTIFICATION OF METHODOLOGICAL CHOICES

In our study, we aim to assess whether there is an association between joint stiffness (uncontrollable exposure) and fear of falling (uncontrollable event). The appropriate study design is therefore that of a prospective cohort with secondary analysis of subgroups within the cohort.

The FES-I is a reference test in geriatrics for assessing fear of falling. Its validity is recognized in geriatrics and for patients with minor cognitive impairment.

Goniometry and the Schober index provide a reliable assessment of joint mobility, with no lack of specificity or sensitivity compared with other joint mobility tests.

To measure the association between fear of falling and joint stiffness, we decided to record them at an instant T (inclusion). These variables may fluctuate within a patient, but it is not the evolution of these parameters that we wish to evaluate, only the implication of one on the other.

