7.3. CARE-RESEARCH DISTINCTION

MANAGEMENT COMPARISON TABLE

| Procedures and treatments | Care-related procedures | Research-related acts |
|---------------------------|-------------------------|-----------------------|
| Hospitalization | X | |
| FES-I questionnaire | | X |
| Hip goniometry | | X |
| Schober index | | X |

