8.1. Research schedule

- Start of inclusion: September 2021
- Length of inclusion period: 6 months
- Duration of each patient's participation: 30 minutes
- Total duration of research: 6 months, can be stopped early as soon as the required number of patients of patients required

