8.4. Visit

The study will take place during the patient's consultation, at which time the study will be proposed to the patient. During the consultation and before any research-related examination, the investigator proposes that the patient to take part in this research and informs him/her of the following in particular:

- the objective, methodology and duration of the study
- Expected benefits
- The computerized processing of data concerning the patient that will be collected in the course of the research, and the patient's rights of access, opposition and rectification.

A copy of the information document is given to the patient prior to participation in the research.

During this visit, the investigator also checks the patient's eligibility criteria. If the patient agrees to participate, he or she gives oral consent during the consultation.

This information is recorded in the patient's medical record.

The non-opposition of the patient will be recorded in the patient's medical file by the investigator or qualified qualified person.

Any amendment that modifies patient management or the benefits, risks and constraints of the research will be the subject of a new information document. The procedure for informing the persons concerned is the same as that described above.

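### Section 6.3 lets the care team suggest who enters, with no consecutive approach and no record of who was passed over, so selection could distort the mobility/FES-I association undetected

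*Combined protocol and SAP*

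**What the plan says.** Section 6.3 (Recruitment procedures) states the entry route: patients are recruited "at the suggestion of the therapeutic team, from among patients cared for by Southern Ile-de-France Hospital Group geriatrics unit". It names who puts patients forward but not on what basis. It also places the check of the inclusion and non-inclusion criteria in the medical file after the patient has been informed and has agreed.

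The other places that bear on entry do not fill the gap:

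- Section 8.4 (Visit): "The study will take place during the patient's consultation, at which time the study will be proposed to the patient". The investigator makes the proposal, but no rule says which patients are reached.
- Section 2.1.4 (duration of the study): "Inclusion and evaluation of patients is carried out progressively over the course of the study". This describes accrual over time, not consecutive approach.
- Sections 6.1 and 6.2 define eligibility, not the order or completeness of approach.
- Section 12.1 lists the data collected. There is no screening log and no count of patients who were not suggested.
- Section 9 compares the three mobility measures between FES-I groups A and B by Mann-Whitney tests, without adjustment and without any analysis of selection.

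Sections 2.3 and 8.2 have stiffness and fear recorded at a single time, inclusion, with no follow-up.

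**The concern.** The study asks one primary question: are mobility and FES-I group associated? Both are observed at one moment in the same patients, so nothing in the design separates how patients got in from what is measured in them. If staff tend to suggest patients who seem both stiff and afraid, an association can appear where none exists. If they tend to suggest patients who seem either stiff or afraid, a reversed association can appear, or a true one can be hidden.

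Because nothing is recorded about eligible patients who were not suggested, the sponsor could not tell afterwards whether any of this had happened. A positive result would be open to the criticism that it reflects referral habits, and a null result to the criticism that referral habits masked a real association.

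**Working it through.** **The plan's own figure.** Section 2.1.4 says "100 patients are required to reject the null hypothesis of the primary objective with 90% power and 5% risk". This cannot be reproduced, because no effect size, standard deviation, group split or sidedness is given. Back-solving for one two-sided Mann-Whitney test at 0.05 (relative efficiency 0.955, share s in FES-I B): d = (1.960 + 1.282) / √(0.955 × 100 × s(1 − s)). This gives d = 0.66 at s = 0.5 and 0.83 at s = 0.2. The selection question does not change N; it concerns what the 100 patients represent.

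**Selection odds ratio.** Let p11, p10, p01 and p00 be the chances of being suggested for patients who are stiff and afraid, stiff only, afraid only, and neither. The odds ratio among suggested patients is the true one multiplied by (p11 × p00)/(p10 × p01). The factor is 1, meaning no bias on this scale, when suggestion depends on one feature only or on the two multiplicatively.

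**From odds ratio to test result.** All inputs here are assumed: no true association, half the patients stiff (mobility below the median), half afraid, N = 100, one two-sided test at 0.05.

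- a = share stiff among suggested afraid patients = p11/(p11 + p01).
- b = share stiff among suggested patients who are not afraid = p10/(p10 + p00).
- n1 and n2 = expected numbers afraid and not afraid among the 100.
- With mobility otherwise random within each half, the Mann-Whitney probability is θ = 0.5 + (a − b)/2.
- z = (θ − 0.5)/√(101/(12 × n1 × n2)).

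| Pattern (p11, p10, p01, p00) | Selection OR | a, b | n1, n2 | z | Positive, formula | Positive, simulation |
|---|---|---|---|---|---|---|
| Equal (0.3 throughout) | 1.0 | 0.50, 0.50 | 50, 50 | 0 | 5.0% | 4.4% to 5.8% |
| Graded (0.6, 0.45, 0.45, 0.3) | 0.6×0.3/0.45² = 0.89 | 0.571, 0.600 | 58.3, 41.7 | −0.24 | 5.7% | 5.2% to 5.5% |
| Both, 1.5 times (0.45, 0.3, 0.3, 0.3) | 1.5 | 0.60, 0.50 | 55.6, 44.4 | 0.86 | 13.7% | 13% to 15% |
| Both, twice (0.6, 0.3, 0.3, 0.3) | 2.0 | 0.667, 0.50 | 60, 40 | 1.41 | 29.1% | 27% to 30% |
| Either, twice (0.6, 0.6, 0.6, 0.3) | 0.5 | 0.50, 0.667 | 57.1, 42.9 | −1.42 | 29.5%, reversed | 29% to 30%, reversed |

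For the fourth row: √(101/(12 × 60 × 40)) = 0.0592; z = 0.0833/0.0592 = 1.41; P(Z > 1.96 − 1.41) is about 0.29. In simulation, selection on stiffness alone gave 5.0% and multiplicative selection on both gave 5.9%.

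**A different selection model.** As a sensitivity check, stiffness and fear were taken as bivariate normal with a logistic chance of being suggested (2000 simulated studies, odds ratios per SD, all assumed).

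- True correlation 0, no selection on either: 4.8% positive. Selection on stiffness only, OR 2: 5.0%.
- True correlation 0, selection on both at OR 2: correlation −0.08 and 9.5% positive. At OR 3: −0.18 and 28%. When far fewer or many more patients are suggested overall, the OR 2 figure is 5.8% or 8.6% and the OR 3 figure 17.9% or 21.3%.
- True correlation 0, an added preference for concordant patients (interaction OR 1.5 to 2): correlation +0.26 to +0.39 and 60% to 94% positive.
- True correlation 0.40: power falls from 89% without selection to 57% with selection on both at OR 2, and to 21% at OR 3.

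Both models show that the direction is not fixed and that the size runs from negligible to large, depending on a pattern the plan neither controls nor records.

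**The case against.** The strongest reply is that the documents never say staff choose on stiffness or fear. Section 6.3 gives no criterion, and the phrase could simply describe who refers eligible patients. The comparison of care and research acts in section 7.3 marks the FES-I, hip goniometry and the Schober index as research acts, and section 12.2 makes the observation notebook the source for all four values. So no formal score need exist when a patient is suggested, and only bedside impressions could act. This stands. A reader might infer that the team knows the hypothesis and selects on the pair under study; the documents support neither step.

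A reader might also infer that any selection on both features biases the result. It does not: multiplicative selection leaves the odds ratio unchanged, and the graded pattern over the same 0.3 to 0.6 range is almost harmless. The 29% figures come from sharply interactive patterns and should not be read as typical.

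Two other passages might seem to add weight but add little. The remark in section 2.1.3 that these patients "are at greater risk of fear of falling" explains the choice of setting, not selection within it. The provision in section 8.1 that the research "can be stopped early as soon as the required number of patients" is an ordinary stop at a fixed number and creates no bias of its own.

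What the objection leaves untouched is that section 6.3 does state an entry route, that this route is discretionary, and that no other section makes approach systematic or recorded.

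**Conclusion.** The point holds as a conditional risk, not a demonstrated bias. The plan admits patients on the care team's suggestion, with no consecutive approach and no record of eligible patients passed over. If informal impressions of stiffness and fear jointly and non-multiplicatively affect who is suggested, the primary association can be created, reversed or hidden, and the planned tests can neither reveal nor repair this.

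Under no true association, with one test at 0.05 and N = 100, the illustrative range is about 5% positive (multiplicative or graded selection), 13% to 15% (selection odds ratio 1.5), and about 29% (2.0, or 0.5 in the reversed direction). Every selection probability behind these figures is assumed, as are the even splits. The change is worth making because it is cheap and protects the only primary comparison.

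**What to change.** In section 6.3, replace suggestion by the team with approach of all patients over 75 in a fixed order until 100 are included: by order of admission in the hospital, and by an order set in advance on each EHPAD resident list (for example room number or alphabetical). State that the medical file is screened against sections 6.1 and 6.2 before approach, as far as the file allows, and change the sequence in 6.3 to match, since it now places that check after agreement.

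Keep a one-line screening log per site with counts of patients approached, ineligible, opposed, and unable to be measured, and report these counts with the results.

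The cost is protocol wording and a short log. N, tests and visit content do not change. More patients will be approached and recruitment within the 6 months may be slower; the documents give no patient flow from which to size this. Selection through opposition, inability to stand, and the rules in section 8.8 for patients who cannot or will not complete a measurement or the questionnaire would remain. The log makes it visible but does not remove it. If fixed-order approach proves unworkable at a site, the log should still be kept, extended to count eligible patients who were not approached, so that readers can judge the selection.
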